Results from the haematology test will be used to generate the eosinophil number. **Note: No eosinophil data collected after screening will be accessible to the site personnel (including the Investigators) to avoid unblinding them to the randomization assignment. To remove the possibility of eosinophil data being calculated from the remaining haematology parameters, data relating to monocytes and basophils collected after screening will also not be provided to site personnel.**

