6.1.2 Blood Eosinophils

Increased eosinophils are associated with increased severity, exacerbations, decreased lung function, and mortality in subjects with asthma (Hospers, Schouten et al. 2000, Garcia, Taille et al. 2013, Talini, Novelli et al. 2015, Price, Wilson et al. 2016). Blood eosinophils have become an established biomarker in inflammatory airway disease (Kostikas, Brindicci et al. 2018).

Absolute numbers of blood eosinophils will be measured using blood collected as part of the automated complete blood count clinical laboratory test which includes a differential count of white blood cells. Results will be reported at the highest precision (level of significant figures) offered by the clinical laboratory. Assessment of blood eosinophils will be conducted at the visits reflected in Section 3.3. The sites will be blinded to eosinophil count.

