12 APPENDICES

Appendix 1 Liver Safety Monitoring and Assessment

Any subject enrolled in a clinical study with active drug therapy that reveals an increase of serum aminotransferases $\geq 3 \times$ ULN or bilirubin $\geq 2 \times$ ULN should undergo detailed testing for liver enzymes using the study Chemistry panel defined in Table 10 which includes ALT, AST, alkaline phosphatase (ALP) and TBL. Testing should be repeated within 48 to 72 hours of notification of the test results. For studies for which a central laboratory is used, alerts will be generated by the central laboratory to inform the Investigator, Sponsor's Medical Monitor, and study team when ALT, AST or TBL exceed the thresholds above. Subjects should be asked if they have any symptoms suggestive of hepatobiliary dysfunction.

Definition of Liver Abnormalities

Confirmed abnormalities will be characterized as moderate or severe by the Investigator where ULN:

	ALT or AST	TBL
Moderate	$>3 \times$ ULN	or
Severe†	$>3 \times$ ULN	and

† Hy's Law Definition: Drug-induced jaundice caused by hepatocellular injury, without a significant obstructive component, has a high rate of bad outcomes, from 10% to 50% mortality (or transplant). The 2 “requirements” for Hy’s Law are:

- Evidence that a drug can cause hepatocellular-type injury, generally shown by an increase in transaminase elevations higher than $3 \times$ ULN (“ $2 \times$ ULN elevations are too common in treated and untreated subjects to be discriminating”).
- Cases of increased bilirubin (at least $2 \times$ ULN) with concurrent transaminase elevations at least $3 \times$ ULN and no evidence of intra- or extra-hepatic bilirubin obstruction (elevated ALP) or Gilbert’s syndrome (Temple 2006).

In addition, the subject should be considered to have severe hepatic abnormalities for any of the following:

- ALT or AST $>8 \times$ ULN.
- ALT or AST $>5 \times$ ULN for more than 2 weeks.
- ALT or AST $>3 \times$ ULN and International Normalized Ratio (INR) >1.5 (If INR testing is applicable/evaluated).

- ALT or AST $>3 \times$ ULN with the appearance of fatigue, nausea, vomiting, right upper quadrant pain or tenderness, fever, rash and/or eosinophilia ($>5\%$).

The Investigator may determine that abnormal liver test results, other than as described above, may qualify as moderate or severe abnormalities, and require additional monitoring and follow-up.

Follow-up Procedures

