Confirmed moderate and severe abnormalities in hepatic functions should be thoroughly characterized by obtaining appropriate expert consultations, detailed pertinent history, physical examination and laboratory tests. The Investigator or designee should complete the liver abnormality case report form (LA-CRF) that has been developed globally and can be activated for any study or another appropriate document (e.g., liver abnormality source consistent with the LA-CRF content). Subjects with confirmed abnormal liver test results should be followed up as described below.

Confirmed moderately abnormal liver tests should be repeated 2 to 3 times weekly then weekly or less if abnormalities stabilize or the study drug has been discontinued and the subject is asymptomatic.

Severe hepatic function abnormalities as defined above, in the absence of another aetiology, may be considered an important medical event and may be reported as an SAE. The Sponsor should be contacted and informed of all subjects for whom severe hepatic liver function abnormalities possibly attributable to study drug are observed.

To further assess abnormal hepatic laboratory findings, the Investigator is expected to:

- Obtain a more detailed history of symptoms and prior or concurrent diseases. Symptoms and new-onset diseases should be recorded as “AEs” on the AE page. Illnesses and conditions such as hypotensive events and decompensated cardiac disease that may lead to secondary liver abnormalities should be noted. Non-alcoholic steatohepatitis is seen in obese hyperlipoproteinemic and/or diabetic subjects, and may be associated with fluctuating aminotransferase levels. The Investigator should ensure that the medical history documentation captures any illness that predates clinical study enrolment that may be relevant in assessing hepatic function.
- Obtain a history of concomitant drug use (including non-prescription medications, complementary and alternative medications), alcohol use, recreational drug use, and special diets. Medications, including dose, should be entered on the concomitant medication page. Information on alcohol, other substance use, and diet should be entered on the LA-CRF or an appropriate document (e.g., liver abnormality page from the source).
- Obtain a history of exposure to environmental chemical agents.
- Based on the subject’s history, other testing may be appropriate including:

- Acute viral hepatitis (A, B, C, D, E or other infectious agents).

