- Ultrasound or other imaging to assess biliary tract disease.
- Other clinical laboratory tests including INR, direct bilirubin.
- Consider gastroenterology or hepatology consultations.
- Submit results for any additional testing and possible aetiology on the LA-CRF or an appropriate document (e.g., liver abnormality page from the source).

Study Discontinuation

In the absence of an explanation for increased liver tests, such as viral hepatitis, pre-existing or acute liver disease or exposure to other agents associated with liver injury, the subject may be discontinued from the clinical study. The Investigator may determine that it is not in the subject's best interest to continue clinical study enrolment. Discontinuation of treatment should be considered if:

- ALT or AST $>8 \times$ ULN.
- ALT or AST $>5 \times$ ULN for more than 2 weeks.
- ALT or AST $>3 \times$ ULN and TBL $>2 \times$ ULN or INR >1.5) (If INR testing is applicable/evaluated).
- ALT or AST $>3 \times$ ULN with the appearance of fatigue, nausea, vomiting, right upper quadrant pain or tenderness, fever, rash and/or eosinophilia ($>5\%$).

In addition, if close monitoring of a subject with moderate or severe hepatic laboratory tests is not possible, clinical study drug should be discontinued.

References

Temple R. Hy's law: Predicting Serious Hepatotoxicity. *Pharmacoepidemiol Drug Saf*. 2006 April;15(Suppl 4):241-3

Guidance for Industry titled "Drug-Induced Liver Injury: Premarketing Clinical Evaluation" issued by FDA on July 2009.

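### Appendix 1 asks the Investigator to grade liver cases partly on eosinophilia, which the blinding rules hide and no written route supplies; the effect is narrow

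*Protocol*

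**What the plan says.** Protocol Appendix 1 makes the Investigator the assessor: "Confirmed abnormalities will be characterized as moderate or severe by the Investigator". Among the findings that make a case severe is ALT or AST above 3 x ULN "with the appearance of fatigue, nausea, vomiting, right upper quadrant pain or tenderness, fever, rash and/or eosinophilia", with the eosinophil limit set at 5%. The same item recurs under Study Discontinuation, in the list introduced by "Discontinuation of treatment should be considered if".

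Section 5.4.6 states: "No eosinophil data collected after screening will be accessible to the site personnel". It names the Investigators as included, and also withholds post-screening monocytes and basophils so that the eosinophil value cannot be worked out. Section 6.1.2 repeats the rule: "The sites will be blinded to eosinophil count". Section 7.5 reserves eosinophil results for unblinded parties until the study has ended and the database is locked. None of the three sections makes an exception for a liver event.

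**The concern.** Two rules in the same protocol conflict. One requires the Investigator to use a laboratory finding; the other denies the Investigator that finding. A subject with a confirmed transaminase rise, no symptoms and new eosinophilia should be severe under Appendix 1, but an Investigator following the protocol would see only the transaminase rise and grade it moderate.

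At stake is the severe grade by rule and what Appendix 1 attaches to it: informing the Sponsor of a severe case possibly attributable to study drug, and possible reporting as an SAE. Section 5.9.1 calls an ad hoc SRC meeting for one SAE judged at least probably related, so the grade can feed that rule indirectly. The specific prompt to consider stopping treatment is also lost, which matters only while doses remain.

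**Working it through.** The plan gives no figure to reproduce. The check sets the texts side by side.

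**1. Is eosinophilia enough by itself?** Yes. Any single item in the severe list suffices, and the features within the item are joined by and/or. Eosinophilia is one of seven features in one of four listed items. Without it, and with no other severe finding, the same case is moderate.

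**2. Can the site derive the value?** No. From the differential the site keeps total white cells, neutrophils and lymphocytes, so it can compute only

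WBC − neutrophils − lymphocytes = eosinophils + monocytes + basophils,

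which is one sum of three unknowns.

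**3. Does any written route supply it?**
- *Liver alert (Appendix 1).* The central laboratory informs the Investigator, the Sponsor's Medical Monitor "and study team when ALT, AST or TBL exceed the thresholds above". Eosinophils are not part of the trigger. The repeat test is the chemistry panel, with no differential named. The text does not say whether the blinded or the unblinded Medical Monitor is meant.
- *SRC (Section 5.8.1).* Eosinophils are kept from its review. It may ask for data to be unblinded, but the text then speaks of breaking the randomization code, which gives treatment and not a laboratory value.
- *Emergency unblinding (Section 7.5.1).* It reveals treatment assignment.
- *Further tests in the liver work-up (Appendix 1) and safety repeats (Section 3.3).* These allow more testing, but Section 5.4.6 bars post-screening eosinophil data from the site without exception, so a site-ordered differential falls under the same bar.
- *Unblinded Sponsor (Section 7.5).* It holds the data but is said to take no part in clinical evaluation, and no text tells it to check eosinophils after an alert.
- *SAP Section 6.2.* It repeats the blinding and adds no route.

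**4. What changes with the grade?** The instruction "Confirmed moderate and severe abnormalities in hepatic functions should be thoroughly characterized by obtaining appropriate expert consultations" covers both grades. The rest differs. The stated retest schedule, two to three times weekly at first, is written for moderate cases; Sponsor notification and possible SAE reporting attach to severe ones. The grade is therefore not a mere label, but a moderate case is still closely followed.

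**5. Would one post-dose sample settle the criterion?** Not always. The criterion concerns newly appearing eosinophilia, and Section 4.1, criterion 5, requires at least 150 or 200 cells/µL at screening, depending on visit and FeNO. The percentage is the eosinophil count divided by WBC. The documents give no WBC values, so I assume 4.0 to 11.0 x 10⁹/L:
- 200/4,000 = 5.0%; 200/11,000 = 1.8%.
- 300/4,000 = 7.5%; 300/11,000 = 2.7%.

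A subject entering at 300 cells/µL is above 5% whenever WBC is below 300/0.05 = 6,000 cells/µL. Some eligible subjects may already exceed the limit before dosing, so the check needs the subject's own baseline, which Section 9.4.1 defines as the last value before the first dose.

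**The case against.** The strongest reply is that little depends on this item. Appendix 1 says that when raised liver tests have no explanation the subject may be discontinued, and that the Investigator may judge continuation not to be in the subject's interest; neither needs eosinophils. Appendix 1 also provides: "The Investigator may determine that abnormal liver test results, other than as described above, may qualify as moderate or severe abnormalities". Section 4.9.2 lets the Sponsor, who holds the data, stop treatment. The eosinophilia item itself asks only that stopping be considered. All of this stands, and it keeps the point small. It does not make the criterion usable: discretion to grade higher does not help an Investigator who cannot see the reason to do so.

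A second reply is that Section 7.5 promises separate documentation of unblinded roles and parameters, and a medical monitoring plan. Those documents may contain a route, and they are not available here. The finding therefore concerns the protocol and SAP text, not how the study was run.

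A third is that releasing the result weakens the blind that Section 5.4.6 protects. That is a fair cost of the fix, not a defence of the conflict.

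A reader might infer that the study's liver stopping rules fail. They do not: the hepatic rules in Section 5.9 rest on ALT, AST and bilirubin, and the only link to eosinophils is the indirect and discretionary SAE path. A reader might also want a rate of affected cases, or to read one from the number of scheduled chemistry draws. The documents give no rate of transaminase elevation or of eosinophilia, and a count of draws does not measure how often the gap would matter.

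**Conclusion.** The point holds in a narrow form. As the protocol is written, one liver-severity criterion, repeated in the treatment-stopping list, cannot be applied by the assessor it names. The consequence arises only for a confirmed ALT or AST above 3 x ULN in which eosinophilia is the sole added feature. Such a case would be graded moderate instead of severe, and would lose the rule-based Sponsor notification, the possible SAE report and the specific prompt to consider stopping. Monitoring and general discretion to stop would remain.

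Confidence is high for what the protocol and SAP say, and does not extend to the separately held documents. The conclusion assumes that the bar in Section 5.4.6 means what it says, including for differentials ordered during a liver work-up. No frequency can be given. This is a low-priority improvement to consider.

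**What to change.** Add to Appendix 1 and Section 7.5 that, on a confirmed ALT or AST above 3 x ULN, the existing unblinded Medical Monitor (or the central laboratory) compares the eosinophil percentage from haematology already scheduled with the subject's pre-dose baseline, and tells the Investigator only whether new eosinophilia above 5% is present. The same edit can say which Medical Monitor receives the liver alert. If the separate unblinding documents already contain such a step, a cross-reference is enough.

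The cost is a short amendment, one instruction on the alert, and a one-line exception to the statement in Section 7.5 that the Sponsor is not involved in clinical evaluation. No new scheduled test is needed: Tables 5 to 8 place haematology at the post-Day-1 chemistry visits (the Table 8 chemistry row is misaligned by a column in the text available, so this reading should be checked against the original), and Section 3.3 allows repeats for safety. The downside is that the yes/no answer may occasionally hint at treatment assignment. Deleting eosinophilia from both lists would avoid that and remove the contradiction, but it gives up a liver feature the sponsor chose to include; that clinical choice is the sponsor's.

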5.4.7 Pregnancy Test and FSH

A β -HCG pregnancy test will be conducted for all female subjects with childbearing potential (as defined in Section 4.8.4) on visit days detailed Table 4 through Table 9 in Section 3.3. A urine pregnancy test will be performed at all visits noted in those tables except on Visit 2 and at the Final Visit when serum pregnancy tests will be performed. Subjects with a positive test result at any Screening visit will be ineligible for enrolment in the study.

In the event a female subject or the female partner of a male subject becomes pregnant during the study, the process described in Section 8.9.8 will be followed. Pregnant female subjects will be withdrawn immediately from the study (as described in Section 4.9.3) and followed as described in Section 8.9.8.

FSH will be assayed in women who on Visit 1 fit the post-menopausal criterion included in Section 4.8.4.

5.4.8 COVID-19 Testing

Subjects will undergo COVID-19 testing as per each site's protocol.

5.4.9 Subject Compliance Assessment

Subject compliance will be assessed by comparing the number of study drug doses the subject received to the number of doses the subject was scheduled to receive as per the protocol.

5.5 Immunogenicity Assessments

Serum samples for the assessment of UPB-101 ADAs and NAbs will be collected as detailed in Table 4 through Table 9 in Section 3.3.

Immunogenicity testing will follow a 3-tiered approach of screening, confirmation, and titration. Any sample screened as positive should be confirmed. Any confirmed positive sample should be titrated and tested for NAb activity and may be further characterized for quantity/titre, isotype, and affinity. Screening, confirmation, and titration assessments should be performed when samples are available; the NAb assay may be conducted later on frozen samples stored until needed.

5.6 Pharmacokinetic Assessments

Timed serum samples will be collected to determine the concentration of UPB-101 and will be collected as detailed in Table 4 through Table 9 in Section 3.3. Pharmacokinetic serum samples will be collected pre-dose on dosing days.

When the PK sampling coincides with the ECG and/or vital sign recordings, priority should be given to the ECGs and vital signs. The actual date and time of each PK sample collection will be recorded in the eCRF.

Blood sample collection, handling, and storage will be described in the laboratory manual.

The PK analyses will be based on the timed blood PK sampling of all enrolled subjects (PK Population). Serum UPB-101 concentrations will be summarized using descriptive statistics and used for PK analyses including the following endpoints if appropriate:

- C_{max} .
- t_{max} .
- AUC_{tau} .
- AUC_{inf} after the first dose, if appropriate.
- $t_{1/2}$, if appropriate.
- CL/F , if appropriate.
- V_z/F , if appropriate.

A power model will be fitted using all doses and across all cohorts to assess dose proportionality for C_{max} and AUC_{tau} after the first dose. Within each dosing regimen, dose proportionality using a comparison of C_{max} and AUC_{tau} after the last dose will also be assessed using descriptive statistics. For each dosing regimen, accumulation of UPB-101 will be assessed by comparing the ratio of C_{max} and AUC_{tau} after the last dose and the first dose for each subject and summarized by dosing regimen.

Analysis of UPB-101 will be performed using a validated method at a bioanalytical laboratory specified by the Sponsor.

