Figure 3	Rotation of Injection Sites.....	74

LIST OF ABBREVIATIONS AND DEFINITION OF TERMS

Ad	admission
ACQ	Subject Asthma Control Questionnaire
ACQ-7	Subject Asthma Control Questionnaire-7
ADA	anti-drug antibody
AE	adverse event
AESI	adverse event of special interest
ALP	alkaline phosphatase
ALT	alanine aminotransferase
AST	aspartate aminotransferase
ATS	American Thoracic Society
AUC _{inf}	area under the concentration-time curve from the time of dosing extrapolated to time infinity
AUC _{tau}	area under the concentration-time curve for one dosing interval
BMI	body mass index
BP	blood pressure
CGI-C	Clinician Global Impression of Change
CL/F	apparent total body clearance after dosing
C _{max}	maximum observed concentration
COVID-19	Coronavirus disease 2019
CPMP	Committee for Proprietary Medicinal Products
CRF	case report form
CRO	contract research organisation
CRP	C-reactive protein
D	day
Di	discharge
ECG	electrocardiogram
eCRF	electronic case report form
EMA	European Medicines Agency
ERS	European Respiratory Society

EU	European Union
EudraCT	European Union Drug Regulating Authorities Clinical Trials Database
FDA	Food and Drug Administration
FeNO	fractional exhaled nitric oxide
FEV ₁	forced expiratory volume in 1 second
FSH	follicle stimulating hormone
GCP	Good Clinical Practice
β-HCG	beta human chorionic gonadotropin
HDL	high density lipoprotein
HED	human equivalent dose
HIV	human immunodeficiency virus
IB	Investigator's Brochure
ICF	informed consent form
ICH	International Council on Harmonisation
ICMJE	International Committee of Medical Journal Editors
ID	identification
IEC	Independent Ethics Committee
IFN λ	interferon gamma
IgE	immunoglobulin E
IgG1	immunoglobulin G1
IL-	interleukin-
INR	International Normalized Ratio
IP-10	interferon gamma-induced protein 10
IV	intravenous
IXRS	interactive response system
LA-CRF	liver abnormality case report form
MedDRA	Medical Dictionary for Regulatory Activities
MHRA	Medicines and Healthcare products Regulatory Agency
Mon	month
NAb	neutralizing antibodies
NOAEL	no observed adverse effect level

PD	pharmacodynamic
PIN	personal identification number
PK	pharmacokinetic
pSTAT	phosphorylated signal transducer and activator of transcription
PT	prothrombin time
PTT	partial thromboplastin time
[REDACTED]	[REDACTED]
[REDACTED]	[REDACTED]
[REDACTED]	[REDACTED]
QFT-G	QuantiFERON®-tuberculosis Gold
QTc	QT interval corrected
QTcF	QT interval corrected using Fridericia's formula
SAD	single ascending dose

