^m At Visit 5 (D2), Visit 6 (D4), Visit 16 (D86), Visit 17 (D88), Visit 18 (D92) and Visit 19 (D99) blood samples for haematology including eosinophils will only be collected for participants enrolled in Cohort 4.

ⁿ At Visit 5 (D2), Visit 6 (D4), Visit 16 (D86), Visit 17 (D88), Visit 18 (D92) and Visit 19 (D99) FeNO will be performed only for participants enrolled in Cohort 4.

^o For subjects enrolled in Cohort 4, Visit 15 (WK12) will be handled as a non-dosing visit. All Visit 15 (WK 12) assessments/activities will be performed as they would on a non-dosing visit. Activities directly related to dose administration and post-dose observation (admission, study drug administration, 4-hour observation, assessment of injection site reactions and discharge) will NOT be performed.

The timing of vital sign, ECG, and spirometric assessments on dosing days is presented in Table 9.

Table 9 Timed Assessments at Each Dosing Visit

Clinical Variable	Pre-dose		Post-dose			
	-60 minutes (±15 minutes)	-30 minutes (±15 minutes)	30 minutes (±15 minutes)	1 hour (±15 minutes)	2 hours (±30 minutes)	4 hours (±30 minutes)
Vital signs	X		X	X		X
Electrocardiogram	X				X	
Spirometry	X	X	X ^a			

^a Spirometry will be obtained 30 minutes after the last injection is administered and may also be conducted at subsequent dosing visits if paradoxical bronchospasm is suspected.

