3.6.3 Cohorts with [REDACTED] Dosing Intervals

The Dosing Period for cohorts with [REDACTED] (e.g., Cohort 3 in Part A) lasts [REDACTED] weeks (Days [REDACTED]). Subjects assigned to this cohort will receive 2 doses of study drug, [REDACTED] weeks apart. The assessments to be conducted on subjects in these cohorts during the Dosing Period and their timing are listed in Table 5 and Table 8.

The [REDACTED] cohorts may include either one or two dosing visits. In cohorts where only 1 dose is administered (such as cohort 4), the participants will undergo the same visits and procedures as those receiving 2 doses, but they will not be admitted to the unit on Day [REDACTED]. The assessments to be conducted on subjects in these cohorts during the Dosing Period and their timing are listed in Table 5 and Table 8.

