4.9 Reasons for Treatment Discontinuation or Study Withdrawal

4.9.1 Duration of Study Participation

Subjects will remain in the study for approximately 9 months. All subjects will undergo Screening for a maximum of 3 weeks. Subjects assigned to a cohort with 3 doses administered [REDACTED] (or 2 doses [REDACTED] if such an interval is selected in Part B) will undergo 2 months of treatment followed by 6 months of observation. Subjects assigned to a 2-dose [REDACTED] regimen will undergo 3 months of treatment followed by 5 months of observation. Subjects assigned to a [REDACTED] regimen (ohort 4) will receive [REDACTED] dose followed by 8 months of observation.

A subject is considered to have completed study treatment if they completed the Dosing Period. A subject is considered to have completed the study if they completed the Dosing and the Observation Periods.

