7.2.4 Cohorts with █ Dosing Intervals

In cohorts with █ dosing intervals, study drug will be administered on Days █ for a █-week Dosing Period, except for Cohort 4 where study drug will be administered on Day 1 ONLY. None of the cohorts with █ dosing are dependent upon the SRC recommendations.

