9.4.8 Pharmacokinetic Analyses

All PK analyses will be conducted using the PK Population. Actual blood sampling time points will be used to evaluate the PK parameters.

Individual concentrations of UPB-101 will be displayed graphically and listed by treatment group. They will be summarized using the number of available observations, the number of values below the lower limit of quantification, mean, median, standard deviation, minimum, maximum, geometric mean, and geometric coefficient of variation (assuming log-normally distributed data). Descriptive statistics of concentrations will be calculated if at least one third of the individual data points are quantifiable (\geq lower limit of quantification).

Dose proportionality information will be obtained by comparing PK parameters of UPB-101 across applicable dose levels. A model will be fitted using all doses and across all cohorts to assess dose proportionality for C_{max} , t_{max} , and AUC_{tau} after the first dose. Within each dosing regimen, dose proportionality using a comparison of C_{max} and AUC_{tau} after the last dose will also be assessed using descriptive statistics.

Immunogenicity, PD biomarkers and clinical outcome measures such as FEV_1 , CGI-C and ACQ-7 will be explored across dose cohorts using dose and exposure-response modelling to assess for dose and/or exposure related trends.

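### The pooled first-dose proportionality model uses AUCtau from cohorts with different dosing intervals, so its AUC slope mixes window length with dose

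*Protocol*

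**What the plan says.** Protocol Section 5.6 states "A power model will be fitted using all doses and across all cohorts to assess dose proportionality for" Cmax and AUCtau following the first dose, and the synopsis has the same sentence. Section 9.4.8 repeats it without the word power and adds tmax: "A model will be fitted using all doses and across all cohorts to assess dose proportionality for" these parameters. The List of Abbreviations defines AUCtau as "area under the concentration-time curve for one dosing interval".

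The interval lengths are redacted, but Section 4.9.1 shows that they differ. Subjects on the three-dose regimen "will undergo 2 months of treatment followed by 6 months of observation", whereas those on a two-dose "regimen will undergo 3 months of treatment followed by 5 months of observation". Cohort 4 is dosed once: Section 7.2.4 has the clause "except for Cohort 4 where study drug will be administered on Day 1 ONLY". It follows the longest-interval schedule, since under Section 3.6.3 "the participants will undergo the same visits and procedures as those receiving 2 doses".

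Only the last-dose comparison is confined to a single regimen. SAP Section 10.9 leaves dose proportionality to a separate PK analysis plan, which was not available for this review.

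**The concern.** AUCtau after a first dose depends on the dose and on how long the area is accumulated. When all cohorts share an interval, the second factor is constant and drops out of the slope. Here it does not. At equal dose, a first-dose area over about 84 days must exceed one over about 28 days. A power model with log dose as its only regressor then assigns part of that difference to dose whenever the longer-interval cohort sits above or below the others on the dose scale.

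Dose proportionality is part of the secondary PK objective, and Section 1.7 says the study's PK data will inform dose and interval modelling for Phase 2. As worded, the AUC slope alone cannot separate a real departure from proportionality from a difference in window length.

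**Working it through.** The plan states no target slope, acceptance range or precision for this model, so there is no figure to reproduce. The check has three steps.

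**1. The intervals.**
- Cohorts 1 and 2: three doses in 2 months (Sections 3.6.1 and 4.9.1). Table 6 has masked study-drug cells at Day 29 and Day 57, so dosing on Days 1, 29 and 57 implies an interval of about 28 days.
- Cohort 3: two doses in 3 months (Sections 3.6.3 and 4.9.1), on the Table 8 schedule. The footnote "For subjects enrolled in Cohort 4, Visit 15 (WK12) will be handled as a non-dosing visit" is needed only if Week 12 (Day 85) is otherwise a dosing visit. Days 1 and 85 imply about 84 days.

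**2. How much larger the longer window is.** Section 1.7 predicts exposure assuming PK that depends on neither dose nor time, so I take the true slope as 1. Assumptions of mine: one compartment, first-order absorption with half-life 3 days, elimination half-life 7, 10 or 14 days. The fraction of AUCinf reached by time T is

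f(T) = 1 − [ka·exp(−kT) − k·exp(−ka·T)] / (ka − k), with ka = ln2/3 and k = ln2/half-life.

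| Half-life | f(28) | f(84) | R = f(84)/f(28) |
|---|---|---|---|
| 7 d | 0.892 | 1.000 | 1.121 |
| 10 d | 0.796 | 0.996 | 1.252 |
| 14 d | 0.682 | 0.980 | 1.437 |

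An absorption half-life of 2 days gives R = 1.095, 1.214 and 1.386; 4 days gives 1.156, 1.299 and 1.498.

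R also has a direct meaning. By superposition, the third-interval area at a 28-day interval is AUC(0–28) + AUC(28–56) + AUC(56–84) = AUC(0–84). So R is the third-dose to first-dose accumulation ratio for that regimen, and the sponsor can insert its own predicted value.

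**3. The fitted slope.** With x = ln(dose) and I = 1 for a cohort on the 84-day window, ln(AUC) = constant + x + I·ln(R). Least squares with equal cohort sizes gives

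slope = 1 + c·ln(R), where c = Σ(x − x̄)I / Σ(x − x̄)².

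For relative doses 1, 2, 3: x = 0, 0.693, 1.099, with mean 0.597. Then c = 0.501/0.617 = 0.812, and at R = 1.252 the slope is 1 + 0.812 × 0.225 = 1.18. All relative doses below are assumed.

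| Relative doses, Cohorts 1, 2, 3 | c | R = 1.10 | 7 d | 10 d | 14 d |
|---|---|---|---|---|---|
| 1, 2, 3 | 0.812 | 1.077 | 1.093 | 1.182 | 1.294 |
| 1, 2, 1 | −0.721 | 0.931 | 0.918 | 0.838 | 0.739 |
| 1, 4, 2 | 0 | 1.000 | 1.000 | 1.000 | 1.000 |
| 1, 2, 3, plus Cohort 4 at 0.25 on 84 d | −0.137 | 0.987 | 0.984 | 0.969 | 0.950 |

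With a common 28-day window, ln(R) disappears and the slope is 1.000 in every row. A separate calculation over half-lives of 7 to 28 days, with bolus-like input or ka = 0.3/day, gave slopes from 0.54 to 1.52 across similar layouts, so the table covers the milder end.

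**The case against.** The strongest case against has four parts.

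- **The governing document has not been seen.** Section 9 presents itself as an outline, and SAP Section 10.9 defers to a PK analysis plan that may set a common window. This stands: the fault is shown in the protocol wording, not in the analysis that will be run.
- **The larger shifts fit the text poorly.** Section 1.7 predicts minimal accumulation. Since R is an accumulation ratio, 1.25 and 1.44 mean 25% and 44% accumulation, which is hard to call minimal. R near 1.10, with slopes of 0.93 to 1.08, fits better. This also stands as a caution on size, although the protocol's accumulation figures are redacted.
- **Imprecision may swamp the shift.** With 6 active subjects in each of three cohorts at relative doses 1, 2, 3, the slope's standard error is SD/√(6 × 0.617) = SD/√3.70. For an assumed between-subject log-SD of 0.2, 0.3 or 0.5, the 95% half-width is about 0.22, 0.33 or 0.55 (t on 16 df, 2.12). A shift of 0.077 is well inside all three; 0.294 is inside the last two but not the first. This limits the practical harm, but a systematic shift that wording can remove should not be left in.
- **Other measures are available.** Cmax, the within-regimen last-dose comparison and the plotted concentrations are free of the problem, and so are first-dose AUCinf and CL/F. But AUCinf and CL/F are planned only where appropriate, CL/F is dose divided by AUCinf and so adds little to it, and neither is a response in the pooled model. They help a careful reader but do not correct the AUC slope that will be reported.

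**Conclusion.** The concern holds. As written, one model is fitted to first-dose areas taken over about 28 and about 84 days, and its AUC slope need not equal 1 under exact proportionality. The intervals are inferred from visible visit days. The direction and size of the effect on the slope cannot be determined, because doses are redacted and no half-life is given. Under the assumptions above, the slope may be unchanged, may move by under 0.1, or may reach 0.74 or 1.29.

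The stakes are modest: a descriptive secondary analysis with no acceptance range, no decision rule and no effect on sample size. It should be fixed because the rule is wrong as worded and the correction is nearly free. Confidence is medium, mainly because the PK analysis plan is unseen. Cohort 4's nominal interval may lie in redacted text; it needs confirming and is not itself counted as a fault.

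**What to change.** In the pooled first-dose power model, replace AUCtau with AUC(0–28 d) for every cohort, including Cohort 4, after confirming that 28 days is the shortest interval. State this in one sentence of the PK analysis plan and match it in the synopsis and Sections 5.6 and 9.4.8. If that plan already sets a common window, only the protocol wording needs aligning.

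- **Sampling:** serum PK is already scheduled on Days 1, 2, 4, 8, 15, 22 and 29 in every regimen, and dosing-day samples are taken pre-dose. In the illustration, a linear-up/log-down trapezoid on these days recovers 97.0% to 97.9% of the 28-day area, the same fraction at every dose, so the slope does not move.
- **Interpolation rule:** specify how the area is brought to exactly 28 days, because the Day 29 window is ±2 or ±3 days. Uncorrected, a sample 2 days early loses 3–5% of the area and one 3 days early loses 4–7%.
- **Keep:** Cmax in the model, and AUCtau for within-regimen comparisons and accumulation ratios.
- **Supportive:** first-dose AUCinf where estimable. In the illustration, 11–32% of it lies beyond Day 28 in Cohorts 1 and 2.
- **Confirm:** Cohort 4's nominal interval wherever AUCtau is still reported for it.

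The cost is wording and a small interpolation step, with no new samples or visits. The pooled model gives up first-dose exposure after Day 28 in the longer-interval cohorts, which stays available in the AUCtau and AUCinf summaries.
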